## STUDY DESIGN AND DURATION

This was a randomized, open-label clinical trial with two treatment arms and a follow-up of two years in patients who received a first deceased-donor kidney transplant. The combinations of immunosuppressors in the study arms were those approved in the technical documentation and used routinely in clinical practice. This was therefore a phase IV clinical trial in the usual conditions of use. The patient recruitment period was 12 months. The minimum follow-up period was 24 months.

**Inclusion criteria:** a) Both male and female patients, 18 years of age or over with no immunological risk (PRA <25% and absence of DSA) who received a first deceased or living donor kidney transplant. b) Patients who for the first three months post-transplant were receiving tacrolimus plus MPA or MMF and steroids and who had stable plasma levels of tacrolimus. c) Absence of clinical or histological immune dysfunction before randomization. d) Absence of de novo DSA at the time of randomization. e) Patients who wished and were able to give their written informed consent to participate in the study. f) Female patients who agreed to use efficient contraceptive methods during the study.

**Exclusion criteria:** a) Recipients of a multiorgan transplant. b) Retransplants. c) Presence of DSA prior to transplant or at the time of randomization. d) Cold ischemia time >30 hours. e) Patients with serum creatinine levels above 2 mg/dL or proteinuria above 1g/day at the time of randomization. f) Previous episode of severe rejection (II-B-III in the Banff/09 classification) before randomization. g) Presence of subclinical rejection in the protocol biopsy before randomization. h) Patients with BK-polyomavirus nephropathy at the time of randomization. i) Patients with recurrent or de novo glomerulonephritis. j) Patients receiving treatment with immunosuppressive drugs other than those of the clinical trial in question. k) Patients who were positive against the human immunodeficiency virus (HIV) or who had a severe systemic infection and who the investigator deems the need for continued therapy. l) Patients who had had any previous malignant disease during the previous five years, except basal cell or excised squamous cell carcinoma.

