**Treatment schedule:**

**Group A: Tacrolimus** 0.15 mg/Kg/day to maintain levels of 8-12 ng/ml for the first two months.

With effect from the third month tacrolimus 0.1 mg/kg/day to maintain levels of 5-8 ng/ml;

**Mycophenolate mofetil (MMF)** 2 gr/day or mycophenolic acid (MPA) 1440 mg/day for the first two weeks post-transplant. With effect from this point MMF 1-1.5 gr/day or MPA 720-900 mg/day; **Steroids:** 0.5 gr of methyl prednisolone intraoperatively and 125 mg on day 1; prednisone 30 mg for the first two weeks post-transplant, then tapering 5 mg/week to reach the dose of 5 mg/day at the second month post-transplant. After this the same dose of prednisone was continued.

This treatment was maintained throughout the whole study period in Group A.

**Group B:** These patients received the same treatment schedule as those of Group A up to the time of randomization (third month post-transplant). After this they received: **Tacrolimus** 0.1 mg/kg/day to maintain levels of 5-8 ng/ml; **MMF** 1-1.5 g/day or **MPA** 720-900 mg/day; withdrawal of steroids between the third and fourth month post-transplant as per usual practice in the center.

Both treatment groups received pre-operatively tacrolimus 0.12 mg/Kg orally and MMF 1 g. or MPA 720 mg. Both treatment groups could receive induction therapy with anti-CD25 monoclonal antibodies (Basiliximab 20 mg iv on days 0 and 4) or polyclonal antibodies (Thymoglobulin 1 mg/kg/day for 4-7 days) in patients at risk of delayed graft function and delayed introduction of tacrolimus.

**Other treatments:** Cases of acute rejection were treated with 3 boluses of 500 mg/day of i.v. methylprednisolone. Cases of steroid-resistant rejection were treated with a standard cycle of 7-10 days of rabbit thymoglobulin. Cases of acute humoral rejection were treated in accordance with the protocol at each center: plasmapheresis, immunoglobulins, and rituximab, either alone or in combination.

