For the measurement of C4d an unstained slide was sent to the reference center, at ambient temperature.

\*The interpretation of the central pathologist was used mainly to analyze the progression of the chronic graft nephropathy. For each patient, the sum of the classification of the chronic lesion was obtained from the 5 histological categories: 1) cg: chronic glomerulopathy. 2) ci: chronic interstitial. 3) ct: tubular atrophy (chronic). 4) cv: arteriolar hyalinosis (chronic). 5) mm: mesangial matrix.

*Confounding variables:* Donor and recipient age, HLA compatibility and PRA, delayed graft function, BMI, CMV infection, concomitant treatment (statins, ACEIs/ARA, beta blockers, diuretics, and ASA), scale of treatment compliance and levels of tacrolimus or CsA.

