#### **Analysis of the lymphocyte subpopulations in peripheral blood by flow cytometry:**

Determinations were done with the same periodicity as for the DSA. Blood samples anticoagulated with EDTA (10 ml) were obtained. A volume of 50 ml was incubated in Falcon polypropylene tubes 12 x 75 mm within 48 hours of extraction with the following monoclonal antibodies: CD4, CD127, CD25, CD183 and CD194 labeled with the fluorochromes FITC, PE, APC, APC-Cy7 and Per-CP. In the window for the CD4+ lymphocytes we studied the expression for the markers CD183 and CD194 and in the window for the CD4 +CD25high CD127 lymphocytes we studied the expression of CD183 and CD194 in the Treg cells. The acquisition and analysis was done in at least 5000 lymphocyte cells with a FACScanto II dual-laser cytometer with FACSdiva software. Each sample of the aspiration cytology underwent the same analysis in a sample of blood anticoagulated with EDTA (3ml) for the comparative analysis.

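### Induction type is missing from the confounder list, so the lymphocyte-subset model and the non-randomised analyses cannot adjust for it

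*Combined protocol and SAP*

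**What the plan says.** **Induction.** Under Treatment schedule, "Both treatment groups could receive induction therapy with anti-CD25 monoclonal antibodies" or a polyclonal antibody. The indication is given as "in patients at risk of delayed graft function and delayed introduction of tacrolimus"; the sentence can be read as applying this to both agents or to the polyclonal one only. Three states are therefore possible: none, anti-CD25, polyclonal. All are settled around transplant, well before randomisation in the third month.

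**Treg measurement.** The flow-cytometry section defines the Treg window by CD4 and "CD25high CD127 lymphocytes we studied the expression of CD183 and CD194 in the Treg cells". CCR4high Treg is one of the subsets named as a secondary variable.

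**Confounder list.** It opens with "Donor and recipient age, HLA compatibility and PRA, delayed graft function, BMI, CMV infection", continues with "concomitant treatment (statins, ACEIs/ARA, beta blockers, diuretics, and ASA" in a closed parenthesis, and ends with "scale of treatment compliance and levels of tacrolimus or CsA". No induction agent appears, and the parenthesis leaves no room to read one in.

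**Use of the list.** The Statistical Analysis Plan refers to confounders once, for the repeated-measures linear model of DSA and lymphocyte subsets. It names no covariates there, so the protocol list is the only definition. For the separate linear regression on de novo DSA, the only factor it names is steroid withdrawal.

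**Sampling times.** Secondary variable (e) lists lymphocyte subsets at months 1, 3, 6, 12, 18 and 24. The flow-cytometry section follows the DSA schedule instead, which is pre-transplant and then months 3, 6, 12, 18 and 24, with no month 1.

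**The concern.** Induction is an immunosuppressive exposure that differs between patients, is fixed before randomisation, and could plausibly act on the lymphocyte populations being counted. The list makes room for statins, diuretics and aspirin but not for this. One of the permitted agents also binds the marker that defines the Treg window, so a low Treg value soon after dosing could reflect the antibody rather than the patient's regulatory cells.

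Two kinds of analysis are affected, in different ways. In the randomised comparison of subsets, an omitted prognostic covariate costs precision and leaves any chance imbalance uncorrected. In the non-randomised analyses, which relate early subsets to later histology and seek risk factors for DSA, induction can act as a true confounder, because nothing has balanced it across the groups being compared.

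**Working it through.** The plan gives no induction rate, sample-size calculation or effect size, so there is no figure of its own to reproduce. From the documents come the numbers randomised (52 and 53), the month-3 randomisation, and the reported correlations. All other inputs below are assumptions.

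**1. Chance imbalance between arms.** Let p be the proportion given induction (assumed 20-80%). The difference in induction use has expectation 0 and SD = √[p(1−p)(1/52 + 1/53) × 105/104].

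- p = 0.2 or 0.8: SD = 7.8 points.
- p = 0.5: SD = 9.8 points.
- Exact hypergeometric probability of a difference of at least 10 points: 14-33%; of at least 20 points: 1-4%.

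**2. What an imbalance does to the arm contrast.** Shift = imbalance × effect of induction on the marker (assumed 0.25-1.0 SD).

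- Smallest: 0.10 × 0.25 = 0.025 SD.
- Largest: 0.20 × 1.0 = 0.20 SD.
- Standard error of a single-time comparison: √(1/52 + 1/53) = 0.195 SD.

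The shift is therefore usually small, and about one standard error at the extreme. An induction effect that stayed constant over time would cancel from the arm-by-time term; one that faded would not.

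**3. Precision.** If induction explains a share R² of subset variance, the standard error is multiplied by √(1−R²): √0.9 = 0.95 and √0.7 = 0.84 for R² of 10% and 30%. Spending 2 of 103 residual degrees of freedom costs √(103/101) = 1.01, giving net factors of 0.96 and 0.84. If induction explains nothing, the loss is about 1%.

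**4. Subset-histology links.** The results report that CCR4highCD4+ cells at month 3 correlate with 24-month interstitial inflammation, r = −0.431, P = 0.007. If this is a Pearson correlation, t = 0.431 × √(n−2)/√(1−0.431²), and P = 0.007 implies about 38 patients. Suppose induction correlates +a with one variable and −a with the other. The partial correlation is (−0.431 + a²)/(1−a²):

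| a (assumed) | partial r | P (n = 38) |
|---|---|---|
| 0.3 | −0.375 | 0.02 |
| 0.4 | −0.323 | 0.05 |
| 0.5 | −0.241 | 0.15 |

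If both correlations had the same sign, the link would strengthen: at 0.3, (−0.431 − 0.09)/0.91 = −0.573. The documents do not allow the reader to tell which case applies.

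**5. DSA risk factors, only if that regression uses the list.** Assume DSA risk of 5% with induction and 10% without, and no true effect of delayed graft function.

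- Induction in 80% of patients with delayed graft function and 30% of others: 0.8×5 + 0.2×10 = 6.0% against 0.3×5 + 0.7×10 = 8.5%, an apparent risk ratio of 0.71.
- Induction in 50% against 30%: 7.5% against 8.5%, ratio 0.88.
- Equal rates: ratio 1.00.

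At 6.0-8.5%, 105 patients yield about 6-9 events, too few to distinguish any of these ratios from chance.

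**The case against.** The strongest reply is that randomisation comes after induction, so the arm comparison is protected. That stands. The chi-square or Fisher comparison of DSA at 24 months is not described as adjusted either, so the primary comparison appears untouched.

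It can also be said that delayed graft function is on the list and stands in for induction. That is partly true. But induction is linked to the risk of delayed graft function, not its occurrence, and a yes/no variable cannot separate three induction states.

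Third, induction is not the only immunosuppressive exposure that varies before randomisation: mycophenolate preparation and dose, and tacrolimus formulation, vary too and are also unlisted. This is correct. What distinguishes induction is the overlap between the anti-CD25 agent and the Treg gate.

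That overlap has limits. It concerns the Treg subset only, and the documents do not say how long the antibody affects CD25 staining. Any month-1 sample precedes randomisation and carries no treatment contrast.

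Finally, the list already holds about 14 items. With few DSA events, more terms in the DSA regression could do harm. This also stands and limits the fix.

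**Conclusion.** The omission is real and worth correcting, at moderate importance. The repeated-measures subset model lacks a relevant baseline covariate. The price is a standard error that adjustment could multiply by about 0.95-0.84 (if induction explains 10-30% of variance) and chance imbalance left in the arm contrast. The subset-histology links are open to confounding of unknown size and direction. All magnitudes rest on assumed induction rates and effects.

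A reader might infer three stronger things that the documents do not support.

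- *That the steroid-withdrawal comparison is biased.* Induction precedes allocation, so the expected imbalance is zero.
- *That the analyses adjust for the wrong exposures.* Tacrolimus level and compliance are relevant and listed. The cyclosporine wording looks like a drafting leftover: neither arm uses the drug, entry requires tacrolimus, and exclusion (j) bars "Patients receiving treatment with immunosuppressive drugs other than those of the clinical trial in question". If nobody takes it, the wording changes no estimate.
- *That the DSA regression will credit delayed graft function with an induction effect.* The SAP does not tie that regression to the list. Its covariates are unspecified, not shown to be wrong.

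**What to change.** 1. Add induction type (none, anti-CD25, polyclonal) to the Confounding variables list and enter it as a baseline covariate in the lymphocyte-subset model, with its interaction with time so that a fading effect is covered.
2. Add a Treg sensitivity analysis by induction type, and report the subset-histology associations with and without adjustment for it.
3. Reconcile secondary variable (e) with the flow-cytometry section on whether month 1 is sampled. If it is, treat the Treg value as pre-randomisation descriptive data outside the arm-by-time contrast.
4. List the covariates of the DSA regression in the SAP, and consider induction there only as far as the number of events allows.
5. Delete the reference to CsA as housekeeping.

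Because preliminary results are already reported, the text should say that the covariate was added after data were seen, and show the unadjusted result beside the adjusted one.

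The cost is 2 degrees of freedom per between-patient comparison, about 1% of the standard error at 105 patients and about 3% at 38 (√(36/34) = 1.03), plus retrieval of induction data from transplant treatment records. Patients are not affected.

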#### **Monitoring of donor-specific anti-HLA antibodies (DSA):**

Monitoring of DSA was done with the Luminex assay and X-MAP technology. The presence of DSA was determined pre-transplant and in months 3, 6, 12, 18 and 24.

Before transplant the presence of anti-HLA antibodies was determined in all the patients by Luminex Mixed, which detects the presence of antibodies against HLA-class I and class II antigens. In positive cases the specificity of the antibodies was determined by Luminex SA (*single antigen*). Likewise, in patients with a high risk of sensitization (previous pregnancy or transfusion) the Luminex SA was also done, even if they had had a negative Luminex Mixed result. Before transplant a serum sample was taken from each patient and frozen in three aliquots of 0.5 ml in Eppendorf tubes.

If the patients had no anti-HLA antibodies pre-transplant, monitoring for these antibodies was done throughout the study using the Luminex Mixed assay. When this assay was positive for any of the measurements established in the study a Luminex SA was done to detect the specificities. If, on the other hand, a patient had a positive Luminex Mixed pre-transplant only the Luminex SA assay was done at all the successive study visits.

Any determination with a mean fluorescence intensity (MFI)  $>500$  was considered positive. All determinations of DSA were centralized at the immunology laboratory of Carlos Haya hospital, Malaga.

All the samples obtained from the various participating centers for determination of anti-HLA DSA were stored at  $-80^{\circ}$  or  $-40^{\circ}$  C until being sent. During transit the samples were stored in dry ice.

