## **STATISTICAL ANALYSIS PLAN.**

Descriptive statistics are presented together with the various analyses. Both an intention-to-treat analysis and an analysis according to the final treatment were done. The categorical variables were analyzed using the chi-square test or Fisher's exact test, according to needs. The quantitative data were analyzed using the Student t test or the Mann-Whitney U test, according to needs. Changes over time in the DSA and lymphocyte subsets in the two study groups were analyzed using a general linear model for repeated measures, adjusting for confounding variables. Correlations between the various subsets were analyzed using Pearson correlation. The graft and patient survival curves were calculated with the Kaplan-Meier method. The rates of survival of the groups were compared with the log-rank test. Finally, a linear regression analysis was done to determine the factors associated with the generation of de novo DSA, including steroid withdrawal. The data were analyzed using SPSS 20.0.

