### **Appearance of donor-specific anti-HLA antibodies (DSA) and acute rejection.**

Steroid withdrawal at the third month post-transplant did not result in the appearance of DSA in patients with a low immunological risk, at least during the first two years of follow-up and using a MFI >500. No significant differences were found in the number of patients who experienced acute rejection after randomization between Group A (7.14%) and Group B (11.54%).

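### The assay route for de novo DSA is set by pre-transplant antibody status, so the planned risk-factor regression cannot separate a sensitisation effect from a difference in detection

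*Combined protocol and SAP*

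**What the plan says.** The section on monitoring of donor-specific antibodies assigns the follow-up assay by pre-transplant status.

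- **Mixed-first route.** For patients with no anti-HLA antibodies before transplant, "monitoring for these antibodies was done throughout the study using the Luminex Mixed assay". Single-antigen testing is conditional: "When this assay was positive for any of the measurements established in the study a Luminex SA was done to detect the specificities".
- **Single-antigen route.** For patients with a positive pre-transplant Mixed result, "only the Luminex SA assay was done at all the successive study visits".
- **Pre-transplant safeguard.** In patients at high risk of sensitisation through pregnancy or transfusion, "the Luminex SA was also done, even if they had had a negative Luminex Mixed result". This is described for pre-transplant testing only.

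The inclusion criteria admit PRA below 25% provided there is no DSA, so both routes can occur among randomised patients. The Hypothesis section names risk factors for de novo DSA as an aim, the Variables section lists PRA among the confounding variables, and the Statistical Analysis Plan states that "a linear regression analysis was done to determine the factors associated with the generation of de novo DSA, including steroid withdrawal". The documents contain no route variable, no single-antigen testing of Mixed-negative follow-up sera, and no sensitivity analysis on this point.

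**The concern.** A patient on the Mixed-first route counts as DSA-positive only if two tests in series are both positive. A patient on the single-antigen route needs only the second. The gate cannot raise detection, and it lowers detection whenever Mixed misses a serum that single-antigen testing would call positive. The protocol's own pre-transplant safeguard makes sense only if such misses occur.

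Because the route follows baseline antibody status, sensitised patients can show more DSA even when their true risk is the same. If PRA or a similar measure enters the regression, its coefficient absorbs that difference. At stake is a detection artefact being reported as a risk factor for de novo DSA.

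**Working it through.** The documents state no DSA rate, assay sensitivity or number of Mixed-positive patients, so there is no planned figure to reproduce.

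**Inputs from the documents.** The two routes (DSA monitoring section); 105 randomised, 52 and 53 per arm (Preliminary Results).

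**Assumptions.** True DSA rate p = 10% in sensitised and unsensitised patients alike. Mixed detects a fraction Se = 0.6 to 0.9 of what single-antigen testing finds. Single-antigen findings are taken as the reference. Between 10% and 30% of patients are on the single-antigen route. Two-sided test at 0.05.

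**Step 1: apparent association with sensitisation.** The detected rate is p on the single-antigen route and p × Se on the Mixed-first route.

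| Se | Single-antigen route | Mixed-first route | Difference | Risk ratio (1/Se) | Odds ratio |
|---|---|---|---|---|---|
| 0.9 | 10% | 9% | 1 point | 1.11 | 0.1111 / 0.0989 = 1.12 |
| 0.6 | 10% | 6% | 4 points | 1.67 | 0.1111 / 0.0638 = 1.74 |

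All of this is artefact, since the true rates were set equal. With one route for everyone (Se = 1) both ratios are 1.00.

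**Step 2: chance of a nominally significant artefact.** Exact enumeration of Fisher's test with 10, 21 or 32 of the 105 patients on the single-antigen route gives these rejection rates:

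- equal detection: 2.0% to 2.8%
- Se = 0.9: 2.7% to 3.7%
- Se = 0.6: 6.4% to 9.4%

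**Step 3: effect of chance route imbalance on the arm comparison.** The standard deviation of the between-arm difference in route share s is √[s(1 − s)(1/52 + 1/53)].

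- s = 0.1: 5.9 points
- s = 0.3: 8.9 points

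The arm difference then moves by p × (1 − Se) × imbalance.

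- Smallest: 0.10 × 0.1 × 5.9 = 0.06 points
- Largest: 0.10 × 0.4 × 8.9 = 0.36 points, or 0.0036 × 53 = 0.19 of a patient in one arm

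**Step 4: missed events, with routes balanced.** Both arms' detected rates are multiplied by s + (1 − s) × Se. Equal rates stay equal and the risk ratio is unchanged, but an absolute difference shrinks. For assumed true rates of 5% and 15%, s = 0.2 and Se = 0.7, the factor is 0.2 + 0.8 × 0.7 = 0.76. The difference falls from 10.0 to 7.6 points, and approximate power falls from 39.7% to 30.8%.

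**The case against.** The strongest reply is that this is a small matter in an exploratory analysis.

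- **The size is assumed.** The odds ratios rest wholly on an assumed sensitivity and rate. This stands, which is why a range is given. The direction follows from the testing sequence.
- **A significant false finding is unlikely with 105 patients.** This also stands: the chance stays below 10% over the range tried. The problem is a biased estimate rather than a probable false positive.
- **The regression covariates are not listed.** That sensitisation enters is inferred from PRA being a named confounder and from the risk-factor aim. The documents do not say how PRA was measured or how closely it tracks Mixed status.
- **There may be few or no events.** The results say that withdrawal did not lead to DSA, "at least during the first two years of follow-up and using a MFI >500", and give no counts. If there were no events, the regression is empty. The wording does not settle this.

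A reader might also infer two stronger claims that the documents do not support.

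- **That the primary result is distorted and its test should be stratified by route.** Route is fixed before randomisation, so neither arm is favoured systematically, and a typical chance imbalance moves the difference by less than half a point. The gate can cost events and power in both arms, but stratifying would not recover DSA that were never detected.
- **That pregnancy or sex would emerge as a risk factor through assay route.** A history of pregnancy does not itself place a patient on the single-antigen follow-up route; under the stated rule a positive pre-transplant Mixed result does. Neither variable is in the listed confounders.

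**Conclusion.** The concern holds for the risk-factor analysis: a sensitisation effect on de novo DSA cannot be told apart from assay route. Under equal true rates of 10% and Mixed detecting 60% to 90% of single-antigen findings, the spurious odds ratio is 1.74 to 1.12, or 4 to 1 percentage points. Those figures depend on the assumed sensitivity and rate, and on a sensitisation measure entering the model. The randomised comparison is essentially unaffected as regards bias. This is a cheap improvement to an exploratory analysis, not a threat to the primary conclusion.

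**What to change.** 1. Define assay route (Mixed-first or single-antigen) from the pre-transplant Mixed result, which the protocol says was obtained in all patients. Add a rule for patients who were Mixed-negative but single-antigen-positive before transplant, whom the monitoring section does not clearly assign to either route.
2. Report DSA counts by arm within route.
3. Run the risk-factor regression in the Mixed-first group, or in all patients with route as a term.
4. State that a PRA or sensitisation coefficient from a model combining both routes is not to be interpreted as a biological risk factor. The same holds for the route coefficient, which carries both sensitisation and detection.
5. Leave the primary test unstratified by route.

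No new assays are needed. The cost is a few lines of analysis-plan text and one derived variable. Since the document already reports results, the change should be labelled post hoc. The downsides are some loss of precision with few events and little remaining sensitisation contrast in the restricted model.
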